**Table 2: Dose Modification and Toxicity Management Guidelines for Immune-related AEs Associated with Pembrolizumab**  
**General instructions:**

1. Corticosteroid taper should be initiated upon AE improving to Grade 1 or less and continue to taper over at least 4 weeks.
2. For situations where pembrolizumab has been withheld, pembrolizumab can be resumed after AE has been reduced to Grade 1 or 0 and corticosteroid has been tapered. Pembrolizumab should be permanently discontinued if AE does not resolve within 12 weeks of last dose or corticosteroids cannot be reduced to  $\leq 10$  mg prednisone or equivalent per day within 12 weeks.
3. For severe and life-threatening irAEs, IV corticosteroid should be initiated first followed by oral steroid. Other immunosuppressive treatment should be initiated if irAEs cannot be controlled by corticosteroids.

Immune-related AEs	Toxicity grade or conditions (CTCAEv4.0)	Action taken to pembrolizumab	irAE management with corticosteroid and/or other therapies	Monitor and follow-up
Pneumonitis	Grade 2	Withhold	
 
Administer corticosteroids (initial dose of 1-2 mg/kg prednisone or equivalent) followed by taper
 
	
 
Monitor participants for signs and symptoms of pneumonitis
 
Evaluate participants with suspected pneumonitis with radiographic imaging and initiate corticosteroid treatment
 
Add prophylactic antibiotics for opportunistic infections
 

	Grade 3 or 4, or recurrent Grade 2	Permanently discontinue		
Diarrhea / Colitis	Grade 2 or 3	Withhold	
 
Administer corticosteroids (initial dose of 1-2 mg/kg prednisone or equivalent) followed by taper
 
	
 
Monitor participants for signs and symptoms of enterocolitis (ie, diarrhea, abdominal pain, blood or mucus in stool with or without fever) and of bowel perforation (ie, peritoneal signs and ileus).
 
Participants with <math>\geq</math> Grade 2 diarrhea suspecting colitis should consider GI consultation and performing endoscopy to rule out colitis.
 
Participants with diarrhea/colitis should be advised to drink liberal quantities of clear fluids. If sufficient oral fluid intake is not feasible, fluid and electrolytes should be substituted via IV infusion.
 

	Grade 4	Permanently discontinue		

AST / ALT elevation or Increased bilirubin	Grade 2	Withhold	
 
Administer corticosteroids (initial dose of 0.5- 1 mg/kg prednisone or equivalent) followed by taper
 
	
 
Monitor with liver function tests (consider weekly or more frequently until liver enzyme value returned to baseline or is stable)
 

	Grade 3 or 4	Permanently discontinue	
 
Administer corticosteroids (initial dose of 1-2 mg/kg prednisone or equivalent) followed by taper
 
	
Type 1 diabetes mellitus (T1DM) or Hyperglycemia	Newly onset T1DM or Grade 3 or 4 hyperglycemia associated with evidence of $\beta$ -cell failure	Withhold	
 
Initiate insulin replacement therapy for participants with T1DM
 
Administer anti-hyperglycemic in participants with hyperglycemia
 
	
 
Monitor participants for hyperglycemia or other signs and symptoms of diabetes.
 

Hypophysitis	Grade 2	Withhold	
 
Administer corticosteroids and initiate hormonal replacements as clinically indicated.
 
	
 
Monitor for signs and symptoms of hypophysitis (including hypopituitarism and adrenal insufficiency)
 

	Grade 3 or 4	Withhold or permanently discontinue 		
Hyperthyroidism	Grade 2	Continue	
 
Treat with non-selective beta-blockers (eg, propranolol) or thionamides as appropriate
 
	
 
Monitor for signs and symptoms of thyroid disorders.
 

	Grade 3 or 4	Withhold or permanently discontinue 		
Hypothyroidism	Grade 2-4	Continue	
 
Initiate thyroid replacement hormones (eg, levothyroxine or liothyroinine) per standard of care
 
	
 
Monitor for signs and symptoms of thyroid disorders.
 

Nephritis and Renal dysfunction	Grade 2	Withhold	
 
Administer corticosteroids (prednisone 1-2 mg/kg or equivalent) followed by taper.
 
	
 
Monitor changes of renal function
 

	Grade 3 or 4	Permanently discontinue		
Myocarditis	Grade 1 or 2	Withhold	
 
Based on severity of AE administer corticosteroids
 
	
 
Ensure adequate evaluation to confirm etiology and/or exclude other causes
 

	Grade 3 or 4	Permanently discontinue		

All other immune-related AEs	Intolerable/persistent Grade 2	Withhold	
 
Based on type and severity of AE administer corticosteroids
 
	
 
Ensure adequate evaluation to confirm etiology and/or exclude other causes
 

	Grade 3	Withhold or discontinue based on the type of event. Events that require discontinuation include and not limited to: Gullain-Barre Syndrome, encephalitis		
	Grade 4 or recurrent Grade 3	Permanently discontinue		

1. Withhold or permanently discontinue pembrolizumab is at the discretion of the investigator or treating physician.

**NOTE:**  
For participants with Grade 3 or 4 immune-related endocrinopathy where withhold of pembrolizumab is required, pembrolizumab may be resumed when AE resolves to  $\leq$  Grade 2 and is controlled with hormonal replacement therapy or achieved metabolic control (in case of T1DM).

**Table 3 Pembrolizumab Infusion Reaction Dose modification and Treatment Guidelines**

NCI CTCAE Grade	Treatment	Premedication at Subsequent Dosing
Grade 1 Mild reaction; infusion interruption not indicated; intervention not indicated	Increase monitoring of vital signs as medically indicated until the participant is deemed medically stable in the opinion of the investigator.	None
Grade 2 Requires therapy or infusion interruption but responds promptly to symptomatic treatment (e.g., antihistamines, NSAIDs, narcotics, IV fluids); prophylactic medications indicated for ≤24 hrs	
Stop Infusion.
 
Additional appropriate medical therapy may include but is not limited to:
 
 
IV fluids
 
Antihistamines
 
NSAIDs
 
Acetaminophen
 
Narcotics
 
 
Increase monitoring of vital signs as medically indicated until the participant is deemed medically stable in the opinion of the investigator.
 
If symptoms resolve within 1 hour of stopping drug infusion, the infusion may be restarted at 50% of the original infusion rate (e.g. from 100 mL/hr to 50 mL/hr).
 
Otherwise dosing will be held until symptoms resolve and the participant should be premedicated for the next scheduled dose.
 
Participants who develop Grade 2 toxicity despite adequate premedication should be permanently discontinued from further study drug treatment
	Participant may be premedicated 1.5h (± 30 minutes) prior to infusion with: Diphenhydramine 50 mg po (or equivalent dose of antihistamine). Acetaminophen 500-1000 mg po (or equivalent dose of analgesic).
Grades 3 or 4 Grade 3: Prolonged (i.e., not rapidly responsive to symptomatic medication and/or brief interruption of infusion); recurrence of symptoms following initial improvement; hospitalization indicated for other clinical sequelae (e.g., renal impairment, pulmonary infiltrates)  Grade 4: Life-threatening; pressor or ventilatory support indicated	
Stop Infusion.
 
Additional appropriate medical therapy may include but is not limited to:
 
 
Epinephrine**
 
IV fluids
 
Antihistamines
 
NSAIDs
 
Acetaminophen
 
Narcotics
 
Oxygen
 
Pressors
 
Corticosteroids
 
 
Increase monitoring of vital signs as medically indicated until the participant is deemed medically stable in the opinion of the investigator.
 
Hospitalization may be indicated.
 
**In cases of anaphylaxis, epinephrine should be used immediately.
 
Participant is permanently discontinued from further study drug treatment.
	No subsequent dosing

Appropriate resuscitation equipment should be available at the bedside and a physician readily available during the period of drug administration.
 
For further information, please refer to the Common Terminology Criteria for Adverse Events v4.0 (CTCAE) at http://ctep.cancer.gov
		

#### **5.4 Concomitant Medications/Treatments**

##### **Permitted Concomitant Medications**

Investigators may prescribe concomitant medications or treatments (e.g., acetaminophen, diphenhydramine) deemed necessary to provide adequate prophylactic or supportive care except for those medications identified as “excluded” as listed below.

##### **Excluded Concomitant Medications**

Subjects must be instructed not to take any medications, including over-the-counter products, without first consulting with the investigator.

The following medications are considered exclusionary during the study. The Principal Investigator must be notified if a subject receives any of these during the study.

- Any investigational anticancer therapy.
- Any concurrent chemotherapy (except as per study), immunotherapy, or biologic therapy.
- Concurrent use of hormones for non-cancer-related conditions (e.g., insulin for diabetes and hormone replacement therapy) is acceptable.
- Immunosuppressive medications including, but not limited to systemic corticosteroids (>10 mg/day prednisone or equivalent), methotrexate, azathioprine, and tumor necrosis factor alpha (TNF- $\alpha$ ) blockers. Use of immunosuppressive medications for the management of investigational product- related AEs, in subjects with contrast allergies is acceptable. In addition, use of inhaled and intranasal corticosteroids is permitted.

#### **5.5 Other Modalities or Procedures/ Research vs. Standard of Care Procedures**

A RT boost is a standard component of RT planning and usually follows WBRT after breast-conserving surgery. In this study, the boost will be administered preoperatively at a dose of 8 Gy for 3 fractions, to begin within 5 days of the second dose of pembrolizumab. RT will be performed using external beam ionizing radiation in accordance with institutional standard practice.

#### **5.6 Duration of Study Participation**

The study duration per subject will be up to 150 days, with up to 14 days of screening, up to 47 days on treatment, and 15 weeks of follow-up after the second pembrolizumab dose.

#### **5.7 Removal of Patients from Protocol**

Patients will be removed from the study when any of the criteria listed in Section 6.5 apply. Notify the Principal Investigator, and document the reason for study removal and the date the patient was removed on the Case Report Form. The patient should be followed-up per protocol.

#### **5.8 Subject Replacement**

Subjects who withdraw from the study treatment prior to starting or during the study intervention and fail to complete the intervention may need to be replaced at the discretion of the study PI. Subjects who complete the study intervention, but are not evaluable for the primary endpoint of tumor infiltrating lymphocytes will also be replaced at the discretion of the study PI.

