## **9.0 STATISTICAL CONSIDERATIONS**

### **9.1 Sample Size**

#### **Phase Ib:**

It is imperative that any experimental pre-operative therapeutic innovation not undermine the timing of curative-intent treatment in localized breast cancer, the primary endpoint for the Phase Ib study is safety/tolerability, as defined by the number of patients who do not necessitate a delay in standard of care treatment (breast surgery or neoadjuvant systemic therapy followed by breast surgery). A small number of patients of TNBC will be included in this cohort to establish safety of the regimen as described below for consideration for further study. Along with safety, assessment of TILs through the course of treatment in this cohort will establish the immunogenicity of this combination. If at least 80% of the first 10 subjects in the TNBC cohort proceed with standard of care therapy without delay, the combination will be deemed safe in the cohort, and enrollment in the HR+ cohort (10 subjects) will occur at that time.

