#### **Phase II:**

Once the protocol has been determined to be safe and the protocol modified accordingly, we will employ Simon's two stage trial design. For this cohort, the null hypothesis that the true response rate is 10% will be tested against a one-sided alternative. In the first stage, 22 patients will be accrued. If there are 2 or fewer responses in these 22 patients, the study will be stopped. Otherwise, 18 additional patients will be accrued for a total of 40 patients. The null hypothesis will be rejected if 8 or more responses are observed in 40 patients. This design yields a type I error rate of 0.04 and power of 0.80 when the true response rate is 25%.

---

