## 9.2 Data Sets Analyzed

### Data Analyses/Study Endpoints

#### 9.2.1 Efficacy Analysis

The primary analysis will be based on an intention-to-treat approach and will include all subjects who receive a dose of study drug.

Phase Ib:

The primary efficacy endpoint will be feasibility as defined by the number of patients who do not necessitate a delay in standard of care treatment. Let  $P_d$  be the true probability that a patient experiences a delay. The trial will stop if there is statistical evidence that  $P_d$  exceeds 20%. We will use a Bayesian sequential design by checking whether  $P_d$  exceeds this threshold value after 3, 6, 9, ... patients are evaluable for feasibility. The decision rule is to stop the trial if the posterior probability that  $P_d$  exceeds 0.20 is 0.95 or more;  $P(P_d > 0.2 | \text{data}) > 0.95$ . A non-informative prior distribution for  $P_d$  will be used. Table 9.2.1 gives the stopping rules for the design at each look and column 2 gives the maximum number of patients with delay in order for the trial to proceed. Stopping rules will also apply for any patients with clinical progression of disease during study treatment, although this is expected to be uncommon. For example, if 4 or more delays in treatment are observed after enrolling 6 patients, the trial stops. The third column gives the probability of stopping the trial when in fact, the true  $P_d = 0.20$ . This is the equivalent of the Bayesian type I error probability. The target type I error probability was set at 0.05.

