**Amendment 11 Changes made in Protocol Version 11 dated 22JUL2020**

1. Study Summary
  - a. For addition of survival status assessment for up to 5 years, study duration changed from "Approx. 1 year" to "Approx. 5 years"
2. Section 4.1 Inclusion Criteria
  - a. Inclusion criterion 4.1.17: Added note to incorporate language from Protocol Clarification Memo dated 30JUN2020 regarding pregnancy testing exemption for egg harvesting patients where due to false positive results lasting for at least two weeks (and therefore are exempt from pregnancy testing within 14 days of C1D1), these subjects may enroll only per investigator discretion.
3. Section 6.1 Study Procedures
  - a. Study Procedures 6.1.10: Added note to incorporate language from Protocol Clarification Memo dated 30JUN2020 regarding pregnancy testing exemption for egg harvesting patients where due to false positive results lasting for at least two weeks (and therefore are exempt from pregnancy testing within 14 days of C1D1), these subjects may enroll only per investigator discretion.
  - b. Section 6.3.6: Added survival status assessment and any evidence of recurrence to be conducted every 6 months for up to 5 years
  - c. Research blood tubes corrected to 3 CPT, 1 red-top tube, and 1 green-top tube of blood.
4. Section 6.4 Time and Events Table
  - a. Added timepoint for survival status assessment and documentation of recurrence for 5 years
  - b. Research blood tubes corrected to 3 CPT, 1 red-top tube, and 1 green-top tube of blood.
5. Section 8.0 Correlatives/Special Studies
  - a. Added description of whole genome/exome sequencing from frozen or FFPE tumor samples.

---

**APPENDIX B: SALGADO CRITERIA FOR TIL SCORE ASSESSMENT****Recommendations for assessing tumor-infiltrating lymphocytes (TILs) in breast cancer**

1. TILs should be reported for the stromal compartment (=% stromal TILs). The denominator used to determine the % stromal TILs is the area of stromal tissue (i.e. area occupied by mononuclear inflammatory cells over total intratumoral stromal area), not the number of stromal cells (i.e. fraction of total stromal nuclei that represent mononuclear inflammatory cell nuclei).
2. TILs should be evaluated within the borders of the invasive tumor.
3. Exclude TILs outside of the tumor border and around DCIS and normal lobules.
4. Exclude TILs in tumor zones with crush artifacts, necrosis, regressive hyalinization as well as in the previous core biopsy site.

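### Section 5.8 allows dosed or TIL-unscorable patients to be replaced at discretion, which does not fit the all-dosed analysis or the fixed 22/40 Simon rule and can bias the first-10 gate

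*Combined protocol and SAP*

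**What the plan says.** Section 5.8 has two replacement rules.

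- Subjects who withdraw before starting or "during the study intervention and fail to complete the intervention may need to be replaced at the discretion of the study PI". The second part of this covers patients who have had a dose.
- Subjects who finish treatment but "are not evaluable for the primary endpoint of tumor infiltrating lymphocytes will also be replaced at the discretion of the study PI". Their feasibility outcome can already be known and their pCR can still be observed.

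No criterion or cap limits the discretion.

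Section 9.2.1 sets the analysis population: "The primary analysis will be based on an intention-to-treat approach and will include all subjects who receive a dose of study drug".

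The decisions are made at set counts. The phase Ib gate in 9.1 reads "If at least 80% of the first 10 subjects in the TNBC cohort proceed with standard of care therapy without delay"; Section 3.0 repeats it and makes it the condition for continuing the TNBC cohort and opening the HR+ cohort. For phase II, 9.1 stops after 22 patients if there are 2 or fewer responses, and otherwise "The null hypothesis will be rejected if 8 or more responses are observed in 40 patients". Section 9.2.1 names pCR as the phase II endpoint. Table 9.2.1 places the Bayesian feasibility looks at 3, 6, 9 and 10 patients, counting those assessable for feasibility, a status that the plan does not define.

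For TIL scoring, Appendix B says "TILs should be evaluated within the borders of the invasive tumor".

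**The concern.** A replaced patient who has been dosed must be either kept or dropped, and the plan's rules fit neither. If kept, the phase II total passes 22 and 40 while the cut-offs stay at 2 and 8. If dropped, the all-dosed rule is broken and the decision rests on patients selected after treatment began. The plan does not say which happens, or whether the replacement takes the vacated place in the 10, 22 or 40.

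The patients concerned are unlikely to be a random sample. Section 5.4 (Toxicities and Dosing Delays/Dose Modifications) ends study treatment when toxicity prevents the second dose, so non-completers can include patients whose timing the feasibility endpoint is meant to capture. A tumour with no invasive component left at Week 7 gives no TIL score under Appendix B, so completers who cannot be scored may include responders. At stake are the phase II error rate, the gate into phase II and the HR+ cohort, and the co-primary TIL comparison.

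**Working it through.** The documents give no replacement rate, so the rates below are assumptions.

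**1. The plan's own figures (9.1, phase II).** Inputs: 22 then 40 patients, stop at 2 or fewer, reject at 8 or more, null rate 0.10, alternative 0.25.

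P(reject) = Σ over x > 2 of P[Bin(22, p) = x] × P[Bin(18, p) ≥ 8 − x].

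- p = 0.10: 0.0398 (plan: 0.04).
- p = 0.25: 0.803 (plan: 0.80).

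The stated design reproduces. So does the phase Ib cumulative stopping probability in Table 9.2.1, 0.042 at a true delay rate of 0.20.

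**2. Replaced patients kept, cut-offs 2 and 8 unchanged.** Same formula at p = 0.10, with stage 1 enlarged roughly in proportion.

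| Stage 1 / total | Type I error |
|---|---|
| 22 / 40 | 0.040 |
| 23 / 42 | 0.051 |
| 24 / 44 | 0.064 |
| 28 / 50 | 0.117 |

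With stage 1 left at 22, the values at 42 and 44 patients are 0.050 and 0.062, so the scaling matters little.

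**3. Replaced patients dropped, none of them reaching pCR.** If a fraction d of dosed patients is replaced and the true all-dosed pCR rate is 0.10, the rate among those counted is 0.10 / (1 − d). Put into the 22/40 rule:

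| d | Rate among counted | Type I error |
|---|---|---|
| 5% | 0.105 | 0.051 |
| 10% | 0.111 | 0.067 |
| 20% | 0.125 | 0.114 |

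**4. Feasibility gate, replaced patients dropped.** Let the true delay rate among all dosed patients be 0.30, the replaced fraction 0.15, and q the delay rate among those replaced. The delay rate among those counted is (0.30 − 0.15q) / 0.85, and the gate is passed with probability P[Bin(10, rate) ≤ 2].

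| q | Rate among counted | P(at least 8 of 10 undelayed) |
|---|---|---|
| 0 | 0.353 | 0.26 |
| 0.30 | 0.300 | 0.38 |
| 0.50 | 0.265 | 0.48 |
| 1 | 0.176 | 0.75 |

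With every dosed patient counted, the probability is 0.38. The gate becomes easier to pass if q is above 0.30 and harder if it is below.

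**5. TILs.** No calculation is possible, because the documents give no rate of absent invasive tumour at Week 7 and no TIL values for such patients. The number of patients is not the difficulty: the power statements in 9.2.1 are written for 8 and 16 evaluable patients, so adding patients to reach those numbers fits them. The difficulty is that the score may be missing because of response.

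**The case against.** The strongest reply is that 5.8 never says a replaced patient leaves the analysis. Read with 9.2.1, a dosed non-completer stays in, and the gap is one of wording. That is a fair reading, and it means the results in steps 3 and 4 describe what could happen, not what the plan prescribes. It does not rescue the Simon rule, because keeping the patients leads to step 2.

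Four stronger readings are tempting, and the documents do not support them.

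- *Feasibility is biased upward.* Section 5.4 ends study treatment after toxicity precisely so that standard care is not held up. Some non-completers may therefore start on time, and step 4 shows that the sign can reverse. The 0.75 figure needs every replaced patient to have been delayed.
- *The Bayesian stopping rule fails once n changes.* The posterior criterion can be applied at any n, and Table 9.2.3 already gives limits up to 20 patients. What remains is that the denominator is undefined.
- *A replacement automatically joins the first 10.* The wording is ordinal, so a later patient does not naturally take an earlier place. The plan should still say so.
- *The best responders are removed from the TIL analysis.* Replacement is discretionary, and Week 7 comes about three weeks after the second dose, whereas surgery in most cases follows chemotherapy. Appendix B also excludes tissue for crush artefact, necrosis and previous biopsy site. Section 9.2.1 has TILs read after the study ends without influence on enrolment, which argues against selection on TIL values. It does not prevent selection through missing tissue, so distortion remains possible but is not shown.

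**Conclusion.** The concern holds as a conflict between 5.8, 9.2.1 and the fixed-n rule in 9.1, and it is more than missing detail: applied as written, the rules can give a phase II test that exceeds its stated error rate. Two extra patients with unchanged cut-offs take type I error from 0.040 to about 0.051. Dropping replaced patients gives 0.051 to 0.114 over an assumed 5% to 20% replacement, if none of them reaches pCR.

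For feasibility, bias arises only if replaced patients are dropped, and its direction is open: 0.26 to 0.75 around a true 0.38, assuming 30% delay and 15% replaced. For TILs, the direction and size are unknown.

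Replacing patients who were never dosed is compatible with 9.2.1 and is not in question.

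**What to change.** - **Section 5.8.** For feasibility and pCR, allow replacement only of patients who never received pembrolizumab.
- **Sections 9.1 and 9.2.1.** State that the 10 (phase Ib) and the 22 and 40 (phase II) are the first that many dosed patients in order of enrolment, whether or not they complete treatment or can be scored for TILs. Count an unknown start of standard care as a delay, and no surgery or an unknown pCR as no pCR. Use the same definition for the denominator at the Bayesian looks.
- **TILs.** If patients are added to reach the evaluable number, report them with all dosed patients for safety and include them in the TIL analysis, but keep them out of the 10/22/40 counts. State this as an explicit exception in 9.2.1, since these patients are themselves dosed. Report how many patients were unscorable because no invasive tumour remained, and repeat the TIL test giving them the best and then the worst rank.

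With every dosed patient counted at fixed n, the printed characteristics stand: Simon type I error 0.040 and power 0.803, and a phase Ib stopping probability of 0.042 at 20% delay.

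The cost is a few sentences in three sections and one sensitivity analysis. Feasibility and pCR may look slightly less favourable.
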